9.4 STATISTICAL ANALYSES

9.4.1 GENERAL APPROACH

Standard statistical conventions will be used, such as statistical hypotheses will be tested controlling the type 1 error rate at 0.05 for 2-sided tests and at 0.025 for 1-sided tests, and p-values less than 0.05 will be considered significant. When confidence intervals are reported 95% confidence intervals will be used. In addition to the formal statistical tests of the primary and secondary endpoints, descriptive summary statistics will be produced. All analyses will be performed by a biostatistician in the University of Colorado Cancer Center Biostatistics Core. The full analysis data set includes all patients who are enrolled onto the trial. The safety data set includes all patients who receive at least one treatment of brigatinib. SAS® software 9.4 M5 (SAS Institute Inc., Cary, NC, USA) or later will be used for the statistical analyses of the study.

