9.2 SAMPLE SIZE DETERMINATION

The goal of this single arm phase 2 trial is to demonstrate specifically the short-term safety and efficacy of a strategy of brigatinib alone for patients with asymptomatic or mildly symptomatic brain metastases. Using contemporary prospective data on brigatinib (Camidge, et al. "Exploratory Analysis of Brigatinib Activity in Patients with Anaplastic Lymphoma Kinase-Positive Non-Small-Cell Lung Cancer and Brain Metastases in Two Clinical Trials" Journal of Clinical Oncology (2018): JCO-2017), our alternate hypothesis (H_1) is that brigatinib alone will result in a CNS disease control rate (DCR) of 90% at 3 months in this population. An upper 1-sided 1-sample exact binomial test with 19 analyzable patients will have 88.5% power to detect a difference between the null hypothesis (H_0) of 60% or less DCR and H_1 , assuming a type-1 error rate of 0.025. Assuming a 20% dropout rate, it is expected that 23 patients would need to be enrolled to yield 19 evaluable patients (i.e. completers).

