9.3 POPULATION FOR ANALYSES

This is a modified intent-to-treat analysis. Patients who enroll and initiate brigatinib and undergo the 3-month (13-week) brain MRI assessment will be analyzed for the study primary endpoint. Secondary endpoints related to safety, tolerability or duration of therapy/progression will be conducted on all who start brigatinib.

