9.4.2 ANALYSIS OF THE PRIMARY EFFICACY ENDPOINT(S)

The primary efficacy endpoint is 3-month Disease Control Rate (DCR) of brain metastases (based on the 13-week MRI), where DCR is defined as complete response (CR), partial response (PR), or stable disease (SD) as defined by the RECIST 1.1 criteria and brain metastases are defined per RANO-BM criteria. A 1-sided 1-sample exact binomial test will be performed to test the null hypothesis (H_0) that $p \leq 0.60$, where p represents the proportion of patients who meet the DCR criteria. With 19 evaluable patients, the test will have 88.5% power to detect an alternative hypothesis value of $p \geq 0.90$ when the type 1 error rate is controlled at 0.025. In addition to the hypothesis test, the proportion of patients meeting the 3-month DCR definition will be summarized using the sample proportion and a 95% exact confidence interval.

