9.4.3 ANALYSIS OF THE SECONDARY ENDPOINT(S)

Secondary endpoints include several time-to-event endpoints: 4 measuring time-to-progression (time-to-CNS PD, time-to-local PD, time-to-distant brain PD, and time until PD at any site), 2 measuring time-to-death (overall and metastases-specific mortality), as well as time-to-administration of WBRT. All time-to-event endpoints will be analyzed using Kaplan-Meier product-limit methods and summarized graphically using Kaplan-Meier survival plots. In

addition, secondary endpoints will be summarized descriptively, including the rates of events, progressive disease, and survival at the follow up intervals (up to 24 months from Day 1). Cumulative rates of best CNS objective response will be described. For QOL, scores from the QLQ-C30 and BN20 will be normalized to 0-100 scales, changes from baseline of ≥ 10 points will be considered clinically meaningful, and cumulative changes at each assessment will be described and time-to-event outcomes for declines in QOL will be summarized graphically using Kaplan-Meier and cumulative incidence plots.

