9.4.6 PLANNED INTERIM ANALYSES

This study is designed to enroll approximately 23 patients in order to yield 19 evaluable patients. Given this relatively small sample size, there are no planned interim analyses for efficacy or futility. After 19 evaluable patients have completed a 3-month brain MRI (allowing for analysis of the primary endpoint of DCR of brain metastases at 3 months), an initial analysis of the primary endpoint and short-term data on secondary endpoints may be performed.

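### Section 9.4.1 sets a p < 0.05 cutoff without limiting it to two-sided tests, at odds with the one-sided 0.025 level of the primary test (minor; no effect at 19 evaluable patients)

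*Combined protocol and SAP*

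**What the plan says.** - Section 9.4.1 (General Approach) assigns type I error rates of 0.05 to two-sided and 0.025 to one-sided tests, then closes the list with a single cutoff: "at 0.025 for 1-sided tests, and p-values less than 0.05 will be considered significant". This is the only p-value cutoff in the plan.
- Section 9.2 (Sample Size Determination) sizes the one-sided exact binomial test "assuming a type-1 error rate of 0.025".
- Section 9.4.2 (primary efficacy analysis) repeats the one-sided exact test of a disease control rate of 60% or less, with power stated "when the type 1 error rate is controlled at 0.025". It adds that the proportion "will be summarized using the sample proportion and a 95% exact confidence interval".
- Section 9.4.3 plans estimation only for the secondary endpoints: "All time-to-event endpoints will be analyzed using Kaplan-Meier product-limit methods and summarized graphically using Kaplan-Meier survival plots", together with descriptive summaries and cumulative incidence plots.
- Section 9.3 lets attendance at the scan determine the primary analysis set: treated patients who "undergo the 3-month (13-week) brain MRI assessment will be analyzed for the study primary endpoint". Section 9.4.6 states the target: "This study is designed to enroll approximately 23 patients in order to yield 19 evaluable patients". The Synopsis caps enrolment at 35, including an allowance for screen failures.

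No section gives the number of successes needed to reject the null hypothesis.

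**The concern.** The first half of the sentence in 9.4.1 and its last clause do not fit together. A one-sided p-value of, say, 0.037 fails the stated one-sided level of 0.025 but passes the stated cutoff of 0.05. Because the one specified test is one-sided, the only written cutoff does not match the test it would be applied to.

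The stake is the verdict on the primary endpoint at the margin. If the last clause were applied to the primary test, a trial could be called positive on a result whose planned 95% exact interval still contains the null rate of 60%. In a small, unblinded, single-arm trial a single patient can decide this, so the decision rule should be readable without inference.

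**Working it through.** **Inputs.** Null rate 0.60, alternative rate 0.90, 19 evaluable patients, one-sided level 0.025, stated power 88.5%, 20% dropout and 23 enrolled (Section 9.2); the p < 0.05 cutoff (Section 9.4.1).

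**Formula.** For n evaluable patients and x successes, the one-sided exact p-value is P(X ≥ x) with X ~ Binomial(n, 0.60). The critical count is the smallest x whose p-value meets the cutoff. Power is P(X ≥ critical count) with X ~ Binomial(n, 0.90).

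**Step 1: the plan's own figure.** At n = 19:

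- 15/19: p = 0.0696
- 16/19: p = 0.0230
- 17/19: p = 0.0055

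No result falls between 0.025 and 0.05, so both cutoffs need 16 successes. Power is P(X ≥ 16 | 19, 0.90) = 0.8850, which reproduces the stated 88.5%.

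**Step 2: nearby evaluable numbers.**

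| Evaluable n | Needed at p ≤ 0.025 (exact size) | Needed at p < 0.05 (exact size) | 95% exact CI at the disputed count |
|---|---|---|---|
| 17 | 15 (0.0123) | 14 (0.0464) | 14/17: 56.6–96.2% |
| 18 | 16 (0.0082) | 15 (0.0328) | 15/18: 58.6–96.4% |
| 19 | 16 (0.0230) | 16 (0.0230) | none |
| 20 | 17 (0.0160) | 17 (0.0160) | none |
| 21 | 18 (0.0110) | 17 (0.0370) | 17/21: 58.1–94.6% |
| 22 | 19 (0.0076) | 18 (0.0266) | 18/22: 59.7–94.8% |
| 23 | 19 (0.0190) | 19 (0.0190) | none |

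Where the cutoffs differ, they differ by one success. In all four disputed cases the lower Clopper–Pearson limit is below 60%, so the literal cutoff and the planned interval would disagree.

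**Step 3: how often the two readings would disagree.** This needs an assumption the plan does not make: 23 patients enrolled, each dropping out independently with probability 0.20, so evaluable n ~ Binomial(23, 0.80). I condition on at least 19 evaluable, the number the Synopsis gives as the minimum; P(n ≥ 19) = 0.501. Given that, P(n = 21) = 0.1864 and P(n = 22) = 0.0678. The chance of opposite verdicts is

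0.1864 × P(X = 17 | 21) + 0.0678 × P(X = 18 | 22).

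- True rate 60%: 0.1864 × 0.0259 + 0.0678 × 0.0190 = 0.0061
- True rate 80%: 0.1864 × 0.2156 + 0.0678 × 0.2108 = 0.0545
- True rate 90%: 0.1864 × 0.0998 + 0.0678 × 0.1098 = 0.0260

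With dropout of 10% and 30% these become 1.2% and 0.3% (true rate 60%), 11.6% and 2.4% (80%), and 5.7% and 1.2% (90%).

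Averaged over n ≥ 19, the type I error under the literal cutoff is 2.3% at 20% dropout, 2.6% at 10% and 2.2% at 30%. Under the 0.025 rule at 20% dropout it is 1.7%.

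Without the at-least-19 condition, at 20% dropout, the readings disagree in 1.4%, 12% and 8.5% of trials at true rates of 60%, 80% and 90%, and the literal cutoff's average type I error is 2.9%.

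All of these are chances that two readings of the text disagree. They are not the chance that this trial reaches a wrong conclusion, because they assume the 0.05 clause overrides the 0.025 statements.

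**The case against.** The best reply is that the documents already settle the matter. The same sentence gives 0.025 for one-sided tests, and Sections 9.2 and 9.4.2 both apply that level to the primary test. A specific section normally governs over a general-conventions clause, and the 95% exact interval corresponds to one-sided 0.025. This stands: 0.025 is the natural reading, and the point is therefore minor.

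A second reply is that the 0.05 clause has a sensible use elsewhere. Section 9.4.1 refers to formal tests of secondary as well as primary endpoints, Section 9.4.4 plans a comparison of adverse events with historical controls, and Section 9.4.8 plans marker correlations. P-values from these would usually be two-sided. This also has some force, but the plan specifies none of those tests, and the clause still does not say it is confined to them.

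A third reply is that the plan is built around 19 evaluable patients, where the cutoffs agree. That is correct, but Section 9.3 takes in everyone with the scan, and the analysis at 19 in Section 9.4.6 is optional. With about 23 enrolled, 21 or 22 evaluable is possible.

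**Conclusion.** The point holds as a minor wording error. The cutoff in 9.4.1 lacks the qualifier that would make it agree with the plan's own one-sided level. There is no effect at 19, 20 or 23 evaluable patients. At 17, 18, 21 or 22 the literal cutoff would accept one fewer success, with exact type I error between 2.7% and 4.6% in place of the stated ceiling of 2.5%.

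With at least 19 evaluable and 20% independent dropout from 23 enrolled, the readings would disagree in about 0.6% to 5.4% of trials at the true rates examined. That range depends on the dropout model and on a reading that is not the natural one. The wording error itself, the exact critical counts and the intervals do not depend on the dropout model.

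**What to change.** Replace the last clause of that sentence in Section 9.4.1 with: two-sided p-values below 0.05 and one-sided p-values at or below 0.025 will be considered significant.

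Optionally, add one sentence to Section 9.4.2 stating that the null hypothesis is rejected when the one-sided exact p-value is at or below 0.025 at the actual number of evaluable patients.

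The cost is one clause, or one clause and one sentence. Design, sample size, stated power and data collection stay as they are.

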9.4.2 ANALYSIS OF THE PRIMARY EFFICACY ENDPOINT(S)

The primary efficacy endpoint is 3-month Disease Control Rate (DCR) of brain metastases (based on the 13-week MRI), where DCR is defined as complete response (CR), partial response (PR), or stable disease (SD) as defined by the RECIST 1.1 criteria and brain metastases are defined per RANO-BM criteria. A 1-sided 1-sample exact binomial test will be performed to test the null hypothesis (H_0) that $p \leq 0.60$, where p represents the proportion of patients who meet the DCR criteria. With 19 evaluable patients, the test will have 88.5% power to detect an alternative hypothesis value of $p \geq 0.90$ when the type 1 error rate is controlled at 0.025. In addition to the hypothesis test, the proportion of patients meeting the 3-month DCR definition will be summarized using the sample proportion and a 95% exact confidence interval.

9.4.3 ANALYSIS OF THE SECONDARY ENDPOINT(S)

Secondary endpoints include several time-to-event endpoints: 4 measuring time-to-progression (time-to-CNS PD, time-to-local PD, time-to-distant brain PD, and time until PD at any site), 2 measuring time-to-death (overall and metastases-specific mortality), as well as time-to-administration of WBRT. All time-to-event endpoints will be analyzed using Kaplan-Meier product-limit methods and summarized graphically using Kaplan-Meier survival plots. In

addition, secondary endpoints will be summarized descriptively, including the rates of events, progressive disease, and survival at the follow up intervals (up to 24 months from Day 1). Cumulative rates of best CNS objective response will be described. For QOL, scores from the QLQ-C30 and BN20 will be normalized to 0-100 scales, changes from baseline of ≥ 10 points will be considered clinically meaningful, and cumulative changes at each assessment will be described and time-to-event outcomes for declines in QOL will be summarized graphically using Kaplan-Meier and cumulative incidence plots.

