1 PROTOCOL SUMMARY

1.1 SYNOPSIS

Protocol Title:

Brigatinib Before Brain Irradiation Trial (B3i Trial): A Phase II Trial of Brigatinib Alone for Brain Metastases from ALK+ Lung Cancer

Objectives:

- ***Primary Objective:***
 1. To evaluate if CNS control is acceptable with a strategy of brigatinib alone for patients with ALK+ lung cancer with brain metastases
- ***Secondary Objectives:***
 1. To evaluate time until progression with brigatinib alone
 2. To evaluate overall survival with a strategy of brigatinib alone
 3. To evaluate the best CNS objective response rates (ORR) with brigatinib alone
 4. To evaluate the time until the administration of WBRT with brigatinib alone
 5. To evaluate longitudinal changes in quality of life with brigatinib alone

Endpoint:

- ***Primary Endpoint:***
 1. Disease Control Rate (DCR) of brain metastases at 3 months (13-week MRI ± 7 days) where DCR is defined as complete response (CR), partial response (PR), or stable disease (SD) as defined by the RANO-BM criteria.
- ***Secondary Endpoints:***
 - 1a. Time until any CNS progressive disease (PD) by RANO-BM criteria and rates at follow up intervals (up to 24 months from Day 1).
 - 1b. Time until any local PD (ie, in brain lesions identified at the time of enrollment) by RANO-BM criteria and rates at follow up intervals (up to 24 months from Day 1).
 - 1c. Time until any distant brain PD (ie, new brain lesions that were not present at the time of enrollment) by RANO-BM criteria and rates at follow up intervals (up to 24 months from Day 1).
 - 1d. Time until progression at any site using RANO-BM for intracranial disease and RECIST for extracranial disease and rates at follow up intervals (up to 24 months from Day 1).

- 2a. Time until death from any cause and rates at follow up intervals (up to 24 months from Day 1).
- 2b. Time until brain metastases-specific mortality, defined as intracranial progression as a component of cause of death and rates at follow up intervals (up to 24 months from Day 1).
3. Cumulative rate of best responses individually for complete response (CR), partial response (PR), stable disease (SD), by RANO-BM criteria
4. Time until the administration of whole brain-radiotherapy (WBRT) and rates at follow up intervals (up to 24 months from Day 1).
5. Quality of life will be assessed using standardized QOL metrics (EORTC QLQ C30/BN 20)

- ***Exploratory:***

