1.3 SCHEDULE OF EVENTS

	Screen/ Enroll	Year 1							Year 2 (Week)				Survival Follow Up
		Day		Week									
Procedures	≤28 days Day 1	Day 1	Day 8 ^c	3 ^c	13 ^d	26 ^e	39 ^e	52 ^e	65 ^e	78 ^e	91 ^e	104 ^e	Termination ^j
Informed Consent/Review Eligibility	X												
Medical History	X												
MRI Brain	X			X	X	X	X	X	X	X	X	X	X
QOL Assessments ^b		X		X	X	X	X	X	X	X	X	X	X
Clinic Visit (complete physical exam)	X	X	X	X	X	X	X	X	X	X	X	X	X
ECOG Performance Status	X	X	X	X	X	X	X	X	X	X	X	X	X
Pregnancy Test (WOCBP only) ^g	X												
Concomitant Meds (including corticosteroids agent and dose)	X	X	X	X	X	X	X	X	X	X	X	X	X
Adverse Events ^h	X	X	X	X	X	X	X	X	X	X	X	X	X
Labs (CBC, CMP, CPK, Lipase, Amylase)	X	X	X	X	X	X	X	X	X	X	X	X	X
Research Blood for cfDNA	X												X
RECIST 1.1/RANO-BM	X			X	X	X	X	X	X	X	X	X	X
Systemic Imaging (CT C/A±P or PET/CT)	X ⁱ			X	X	X	X	X	X	X	X	X	X
Brigatinib Administration ^a		X	X	X	X	X	X	X	X	X	X	X	
CNS Radiation for Brain Metastases Progression (as indicated per PI/Sub-I)													X ⁱ
Vitals Collection (BP, spO ₂ and HR)	X	X	X	X	X	X	X	X	X	X	X	X	X
Survival and Disease Status, Current Therapy													X

3-month intervals are defined as 13 weeks (52 weeks per 12 months / 4)

^a All patients will be started on brigatinib 90 mg daily for 7 days, before escalating to 180 mg daily thereafter as tolerated

^b EORTC QLQ-C30 and BN20 brain-specific questionnaire

^c Day 8 and Week 3 procedures have a window of \pm 4 days from Day 1

^d Week 13 procedures have a window of \pm 7 days

^e All time points 26 weeks and onwards inclusive have a window of \pm 14 days

^f For patients removed from study treatment prior to 24 months (Week 104), survival follow-up will be done every 6 months (\pm 14 days from Termination Visit) for up to 24 months from Day 1, or until death or patient withdrawal of consent; this includes for patients who develop CNS progression while on study

^g Pregnancy Test (for WOCBP only) should also be performed prior to any radiation therapy subsequent to enrollment including radiation for brain or extracranial disease according to SOC.

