2.2 BACKGROUND

Brain metastases (BM) are a significant problem for patients with non-small cell lung (NSCLC) driven by anaplastic lymphoma kinase (ALK) gene rearrangements. Up to 30-40% of ALK NSCLC patients will present with BM at diagnosis and over 70% will ultimately develop BM (Rusthoven 2016). Crizotinib, a first-generation ALK inhibitor has demonstrated relatively poor CNS penetration and limited CNS activity (Costa 2015). As a result, historically, ALK+ NSCLC patients treated with crizotinib who developed BM were treated with early administration of CNS radiotherapy (RT) as the standard of care.

CNS RT is effective at treating BM but can significantly affect quality-of-life (QOL) and cognitive function. In the EORTC 22952-26001 trial, the use of WBRT was associated with inferior global QOL at 9 months and inferior cognition at 1 year compared to radiosurgery alone (Soffieti 2011). In the NCCTG-N0574, WBRT was associated with an objective decrease in cognition at 3 months, which persisted for 1 year in long term survivors (Brown 2016).

Brigatinib is a next-generation TKI with FDA approval for the treatment of metastatic ALK NSCLC. Brigatinib has notably demonstrated promising central nervous system (CNS) activity in the treatment and prevention of BM. In a multicenter phase II trial, brigatinib provided an intracranial objective response of 67% in crizotinib-refractory patients with measurable BM at enrollment (Kim 2017). In a phase 3 trial comparing brigatinib to a crizotinib, the intracranial response rate for measurable BM at enrollment was 78% with brigatinib vs 29% with crizotinib (Camidge 2018). The observation of high intracranial ORRs with brigatinib raises the possibility of a new paradigm for the treatment of patients with ALK+ NSCLC brain metastases with drug alone and reserving CNS RT for patients who subsequently develop CNS progression.

Prospective investigations of CNS RT de-intensification strategies are particularly important for ALK+ NSCLC, where patients are often younger at diagnosis and experience prolonged median survival of >4 years after the identification of brain metastases, which is more than long enough to manifest potential cognitive sequelae from CNS RT. For example, in a multi-institutional study of ALK+ NSCLC treated in the crizotinib era, the median OS was 49.5 months post BM; 50% required ≥ 2 courses of RT, 25% required ≥ 3 courses of RT, and 50% required WBRT (Johung 2016).

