4 STUDY DESIGN

4.1 OVERALL DESIGN

This is a single arm phase-II study including patients with ALK+ NSCLC and brain metastases, who are either neurologically asymptomatic or have only mild neurologic symptoms (RTOG acute neurologic morbidity score 0-2) from their brain metastases, who are TKI naïve or have had prior exposure to crizotinib, but who are naïve to brigatinib and other ALK TKIs including alectinib, lorlatinib, and ceritinib. At screening and enrollment, patients will have a history and physical exam, CTCAE symptoms assessment, and brief QOL questionnaires.

At day 1, all patients will be started on brigatinib 90 mg daily for 7 days, before escalating to 180 mg daily thereafter as tolerated.

At day 8, patients will be seen for a scheduled clinic visit. Each clinic visit will include toxicity assessment and physical exam. Day 8 procedures have an allowable window of ± 4 days. Brief QOL questionnaires will be administered at baseline (Day 1), at 3 weeks (Day 21), and at 3 months (week 13) and subsequent visits every 3 months.

At 3 weeks (Day 21), patients will be seen for scheduled clinic visits and a scheduled surveillance brain MRI. Week 3 procedures have an allowable window of ± 4 days. Subsequently, patients will have scheduled clinic visits and surveillance brain MRIs at 3 months post enrollment (week 13) and at 3 month intervals for year 1 and 2 (ie, at week 26, 39, 52, 65, 78, 104).

Patients who develop CNS progression during the study will be offered palliative radiation for their brain metastases and their disease status will be recorded as CNS progression event.

Patients who experience disease progression per RECIST 1.1 or RANO BM may continue to be treated with brigatinib if, in the opinion of the treating investigator, they continue to experience clinical benefit. Note, this is an accepted treatment strategy per the contemporary NCCN NSCLC guidelines. In this case, patients will be removed from study treatment and will be followed for survival for up to 24 months from Day 1, but may continue to receive brigatinib per standard of care.

If patients do not experience disease progression, they will complete the study treatment at 24 months. Patients continuing to benefit from brigatinib in the opinion of the treating physician may remain on the drug after 24 months per standard of care.

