9 STATISTICAL CONSIDERATIONS

9.1 STATISTICAL HYPOTHESES

- Primary Efficacy Endpoint(s):
Disease Control Rate (DCR) of brain metastases at 3 months (13-week MRI), where DCR is defined as complete response (CR), partial response (PR), or stable disease (SD) as defined by the RANO-BM criteria. The primary analysis will test the following hypotheses:

$$H_0: p \leq 0.60$$

$$H_1: p \geq 0.90$$

where p represents the proportion of patients who meet the DCR criteria.

- Secondary Efficacy Endpoint(s):
 - 1a. Time until any CNS progressive disease (PD) by RANO-BM criteria
 - 1b. Time until any local PD (ie, in brain lesions identified at the time of enrollment) by RANO-BM criteria
 - 1c. Time until any distant brain PD (ie, new brain lesions that were not present at the time of enrollment) by RANO-BM criteria
 - 1d. Time until progression at any site using RANO-BM for intracranial disease and RECIST for extracranial disease
 - 2a. Time until death from any cause
 - 2b. Time until brain metastases-specific mortality, defined as intracranial progression as a component of cause of death
 3. Cumulative rate of best responses for complete response (CR), partial response (PR), stable disease (SD), by RANO-BM criteria
 4. Time until the administration of whole brain-radiotherapy (WBRT)
 5. Quality of life will be assessed using standardized QOL metrics (EORTC QLQ C30/BN 20)
- Exploratory Endpoint(s):
 1. Quantification of corticosteroid agent and dose at screening and at each clinical assessment

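### Kaplan-Meier is planned for six secondary endpoints in which death is a competing event, so 1 − KM can overstate the proportion of patients affected; the effect is small

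*Combined protocol and SAP*

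**What the plan says.** Section 9.4.3 lists seven time-to-event secondary endpoints: four for progression, two for mortality, and time to WBRT. One method is set for all of them: "All time-to-event endpoints will be analyzed using Kaplan-Meier product-limit methods and summarized graphically using Kaplan-Meier survival plots". The same paragraph adds a descriptive summary that includes "the rates of events, progressive disease, and survival at the follow up intervals (up to 24 months from Day 1"), with no estimator named for those rates. Cumulative incidence plots appear once, for quality-of-life decline, and are not extended to the seven endpoints.

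The definitions are in Sections 1.1, 3 and 9.1. Endpoints 1a–1d are times to progression, for example "Time until any local PD (ie, in brain lesions identified at the time of enrollment) by RANO-BM criteria". Endpoint 4 is time to WBRT. Endpoint 2b is "Time until brain metastases-specific mortality, defined as intracranial progression as a component of cause of death". None of 1a–1d or 4 includes death in the event, and 2b leaves out deaths without intracranial progression as a component of cause. Only 2a, death from any cause, counts every death. No censoring rule is given.

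On population, Section 9.3 says: "Secondary endpoints related to safety, tolerability or duration of therapy/progression will be conducted on all who start brigatinib". Section 9.2 expects about 23 enrolled patients.

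**The concern.** A patient who has died can no longer progress, receive WBRT or die of brain metastases. If death is not part of the event, Kaplan-Meier has to censor it, and so treats the patient as if the event could still occur later. The complement of the curve then estimates a risk in a hypothetical setting without those deaths. That is at least as large as the proportion of patients who have the event, and larger whenever target events occur after an event-free death.

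Endpoint 2b is the plainest case, because other-cause death is by definition the alternative outcome. Endpoint 4 is close behind. Section 6.1.1 allows radiosurgery or partial-brain radiotherapy at CNS progression, so a patient can progress and die without WBRT, and deaths after progression compete as well.

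These endpoints describe how often patients on drug alone later have CNS failure, need WBRT or die with brain disease as a cause. Readers will take curves and interval rates as proportions of patients. The error runs one way, towards overstating those outcomes.

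**Working it through.** **Plan's own figure.** The documents state no figure for the secondary time-to-event endpoints. The stated primary design reproduces: with n = 19, p0 = 0.60 and p1 = 0.90, success at 16 or more gives exact one-sided alpha 0.0230 and power 0.885, matching the 88.5% in Section 9.2. That test does not use the time-to-event methods.

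**Inputs from the documents**
- Follow-up: 24 months from Day 1 (Section 4.4).
- Patients: about 23 (Section 9.2).
- Mortality: "the median OS was 49.5 months post BM" (Section 2.2), from a crizotinib-era study and the only survival figure given.

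**Assumptions**
- Constant hazards.
- 24-month Kaplan-Meier event rates of 15% and 30%, since the documents give none.
- An event-free death hazard equal to m times the overall death hazard, with m = 0.25, 0.5 or 1. The value 1 is an upper end on this survival figure: only deaths before the event compete, and worse clinical status already counts as progression in the RANO-BM table in Section 8.1.1.

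**Formulas**
- Overall death hazard: d0 = ln 2 / 49.5 = 0.0140 per month. Deaths by 24 months: 1 − exp(−24 × 0.0140) = 28.5%.
- Event hazard: h = −ln(1 − KM24) / 24. For KM24 = 30%, h = 0.0149; for 15%, h = 0.0068.
- Competing hazard: d = m × d0.
- True proportion with the event: CIF24 = h/(h + d) × [1 − exp(−24(h + d))].
- Event-free deaths: d/(h + d) × [1 − exp(−24(h + d))].

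**Results for 1a–1d and 4**

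| KM24 | m | CIF24 | Excess of 1 − KM (points) | Event-free deaths among 23 |
|---|---|---|---|---|
| 30% | 0.25 | 28.8% | 1.2 | 1.6 |
| 30% | 0.5 | 27.8% | 2.2 | 3.0 |
| 30% | 1 | 25.7% | 4.3 | 5.6 |
| 15% | 0.25 | 14.4% | 0.6 | 1.7 |
| 15% | 0.5 | 13.8% | 1.2 | 3.3 |
| 15% | 1 | 12.8% | 2.2 | 6.1 |

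**Results for 2b.** Let s be the share of deaths that are brain-metastasis-specific. Then KM = 1 − exp(−24 × s × d0) and CIF = s × [1 − exp(−24 × d0)].

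| s | KM | CIF | Excess (points) |
|---|---|---|---|
| 25% | 8.1% | 7.1% | 0.9 |
| 50% | 15.5% | 14.3% | 1.2 |
| 75% | 22.3% | 21.4% | 0.9 |

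**Small-sample check.** A simulation with 23 patients, 5,000 runs, KM24 = 30% and no other censoring gives a mean excess of Kaplan-Meier over Aalen-Johansen of 1.2, 2.3 and 4.2 points for the three values of m. The standard deviation of the Kaplan-Meier estimate is about 10 points.

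**Yardstick.** The 95% half-width around 30% with 23 patients is 1.96 × √(0.3 × 0.7 / 23) = 0.187, about 19 points.

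**Wider range.** With m = 1 and a 70% event rate, more plausible for any-site progression than for WBRT, the excess is 8.6 points. That is still below one standard error (√(0.7 × 0.3 / 23) = 9.6 points). If 40–50% of patients died by 24 months and the whole death hazard were event-free, the excess would be about 6–16 points for event rates of 30–70%. That goes beyond what the protocol's survival figure implies.

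**The case against.** The strongest objection is weight. In the central case (30%, m = 0.5) the excess is 2.2 points, about half a patient in 23, and no hypothesis test or decision rule hangs on these endpoints. That stands as a statement of size. It does not make Kaplan-Meier the right estimator, and for a descriptive endpoint the estimate is the whole result.

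Second, censoring deaths is a common convention for time to progression and is valid for the cause-specific hazard. That is true, but it does not turn 1 − KM into a proportion of patients, and it offers little defence for 2b.

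Third, the plan never says that 1 − KM will be reported, and the interval rates might be simple proportions. With complete follow-up to the time point, those would equal the cumulative incidence and carry no bias. This is fair: for the rates, the fault is that no estimator is named. The curves remain affected.

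Fourth, the size rests on assumed event rates and one range of multipliers, although competing mortality will differ between endpoints. This also stands. Small is a judgement on the protocol's own survival figure and not a guarantee.

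Finally, adding death to the event would also be coherent, most naturally for 1d, but it would change the endpoint from time to progression to progression-free survival.

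**Conclusion.** The concern holds. Followed as written, Section 9.4.3 censors event-free deaths for 1a–1d and 4, and other-cause deaths for 2b. Censoring is inferred, since no rule is stated, but Kaplan-Meier leaves no other handling once death is outside the event.

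On the protocol's survival figure with constant hazards, the overstatement at 24 months is about 1–4 points at an event rate of 30%, about 1 point for 2b, and at most 8.6 points at a rate of 70%. It would be larger only with clearly higher event-free mortality. All of these are below sampling error with 23 patients. The primary analysis, sample size and power are not affected. The change should be made because it gives a correctly defined estimate at almost no cost, with a method the plan already names for quality of life.

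**What to change.** In Section 9.4.3, keep Kaplan-Meier for overall survival (2a). For 1a–1d, 2b and 4, report Aalen-Johansen cumulative incidence with 95% confidence intervals, with death as the competing event (other-cause death for 2b). Name the same estimator for the rates at follow-up intervals, and state the censoring rules.

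A related clarification can go into the same edit. One patient can have both local and distant brain progression (1b and 1c). Section 4.1 says that, if brigatinib is continued after progression, "patients will be removed from study treatment and will be followed for survival for up to 24 months from Day 1", and under the Section 1.3 footnote for patients removed from treatment before 24 months, "survival follow-up will be done every 6 months". That schedule does record disease status and current therapy, but the plan does not say whether one type of CNS progression is still assessed after the other. State whether 1b and 1c are overlapping endpoints with continued assessment or first-site-of-failure endpoints. One should not simply be censored at the other.

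The cost is a few sentences of SAP text and a small amount of programming on data already planned. No patients or visits are added; continued assessment under 1b and 1c needs extra imaging only if the sponsor chooses it.
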